14.3. Analysis Populations

Safety Population:

All Subjects who were administered any test article excluding Subjects who drop out prior to administering any test article. At least one observation should be recorded.

Per-Protocol Population:

All Subjects who have successfully completed all visits and did not substantially deviate from the protocol as determined by the trial cohort review committee prior to database hard lock (Per-Protocol Population). Justification of excluding Subjects with protocol deviations in the per-protocol population set will be documented in a memo to file.

Intent-to-Treat (ITT) Population:

All Subjects regardless of actual treatment and subsequent withdrawal from study or deviation from protocol. At least one observation should be recorded.

14.4. Level of Statistical Significance

All planned analysis for this study will be conducted with an overall type I error rate of 5%.

14.5. Primary Analysis

Likelihood to be a successful lens wearer vs. Quest questionnaire classification

The successful lens wear will be converted to a binary response the same as in the previous analysis. The proportion of response (“1”) will be analyzed using a generalized linear mixed model with a binary distribution and logit link function for all questions. Each model will include the experimental design factors: Quest questionnaire classification as the fixed effect; and subject as the random effect. Other baseline characteristics known to be important such as age, sex, and/or add power will be included as fixed covariates when appropriate.

The proportion of successful lens wear for the subjects classified as being “discontented and driven” will be calculated with 95% CI for least square mean. If the lower limit of the CI is greater than 75%, the statistical superiority will be concluded.

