2. STUDY OBJECTIVES, ENDPOINTS AND HYPOTHESES

2.1. Objectives

Primary Objective(s):

To determine if the QUEST questionnaire, collected at baseline, are significantly correlated with subject groups that are classified as being 'likely to be successful' and/or 'likely to be unsuccessful' after wearing an investigational multifocal contact lens.

Secondary Objective(s):

To determine if certain physical ocular related data is significantly correlated with subject groups that are classified as being ‘likely to be successful’, ‘likely to be unsuccessful’ after wearing an investigational multifocal contact lens.

Likely to be Successful Group definition:

- Completed study, AND ...
- Investigator would recommend the study CLs, AND ...
- The subjects’ response on the MRD “overall quality of vision” and “overall comfort” questions as good, very good, or excellent.

Likely to be Unsuccessful Group definition:

- Not meeting the definition of successful.

Exploratory Objective(s):

BIG 5 Personality Assessment

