***Likely to be Successful Group definition:**

- Completed all required study visits, AND ...
- Investigator would recommend the study CLs, AND ...
- The subjects' response on the MRD "overall quality of vision" and "overall comfort" questions as good, very good or excellent.

Likely to be Unsuccessful Group definition:

- Not meeting the definition of successful.

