2.3. Hypotheses

Primary Hypothesis

- At least 75% of the subjects who are classified by Quest questionnaire as being "discontented and driven" will be in the "likely to be successful" group. The Quest questionnaire will be collected at baseline.

Secondary Hypothesis

- At least one of the secondary endpoints will be significantly correlated with the success classification of the subjects after adjusting for age, sex and ADD power.

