14.2. Sample Size Justification

This is an exploratory study to generate initial data for assessing a computational vision model. As such, the sample size was not determined based on any power analysis with regard to the primary endpoint. The collected data will be used to design future studies, if necessary.

The planned sample size (75 to enroll and 50 to complete) was selected to enroll different categories of myopic presbyopes including previous MF CL wearers, Single vision CL wearers and Subjects who are neophyte to CL wear. Efforts will be made to enroll subjects in all three categories without specific targets to be achieved.

All analysis will be conducted on the per-protocol population defined in section 14.3.

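### The primary model fits a subject random effect to one yes/no per subject, leaves fitting and degrees of freedom open, and its logit-Wald interval cannot pass an all-success class

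*Combined protocol and SAP*

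**What the plan says.** Section 14.5 converts success to a binary response and analyses it with a generalized linear mixed model, logit link, with "Quest questionnaire classification as the fixed effect; and subject as the random effect". Age, sex and add power may be added as covariates. For the discontented-and-driven class, the proportion successful "will be calculated with 95% CI for least square mean", and the rule is: "If the lower limit of the CI is greater than 75%, the statistical superiority will be concluded". This tests the primary hypothesis in 2.3, which begins "At least 75% of the subjects who are classified by Quest questionnaire as being".

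Section 2.2 defines success as a composite: "Completed all required study visits, AND" the investigator would recommend the lenses, and the subject rates both overall vision and overall comfort on the MRD as good or better. Anyone else is unsuccessful.

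Section 14.2 adds: "All analysis will be conducted on the per-protocol population defined in section 14.3". Section 14.3 limits that set to subjects who completed all visits. Kenward-Roger degrees of freedom appear only in 14.6, for the secondary analysis. No section names an estimation method, the scale of the interval, a conditional or marginal mean, or what to do if the variance cannot be estimated or a class has no failures.

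**The concern.** A subject random effect needs repeated outcomes within subject. Here each subject supplies one 0 or 1. The subject variance is therefore not identifiable without covariates and practically unidentified with them.

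If software reports a non-zero variance, the conditional least-squares mean no longer equals the class proportion in hypothesis 2.3. If it reports zero, the random effect does nothing and the verdict rests on the interval. The ordinary interval for a least-squares mean from a logit model is Wald on the logit scale, back-transformed. It breaks down when every subject in the class succeeds, so the best possible result cannot meet the rule.

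The completers-only set makes an all-success class more likely. Subjects who stop, including those discontinued at Visits 4 or 5 for unacceptable vision, leave the analysis although 2.2 calls them unsuccessful. Completers can still fail on either MRD rating or on the recommendation. At stake is a wrong reading of hypothesis 2.3, carried into the future studies that 14.2 says these data may inform.

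**Working it through.** The plan gives no power or target count for this test (14.2), so there is no figure to reproduce. Inputs from the documents: threshold 75%, two-sided 95% interval, about 50 completers. Class size is not given; 10 to 50 is assumed. True rates and random-effect SDs are illustrative.

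**1. Random effect, likelihood fit.** With one record per subject, the class likelihood depends only on the marginal success probability, so any SD fits equally well once the intercept is re-solved. For 35/40 the log-likelihood is 35 ln(0.875) + 5 ln(0.125) = −15.071 at every SD. The conditional lower limits by Gauss-Hermite quadrature and the delta method are:

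| SD | Lower limit | Verdict |
|---|---|---|
| 0 | 73.3% | fail |
| 0.5 | 74.5% | fail |
| 1 | 77.5% | pass |

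**2. Random effect, restricted pseudo-likelihood.** The Kenward-Roger reference concerns restricted likelihood, which points to this route. It was fitted, intercept only, to 229 outcomes with n = 20 to 50. The fitted variance was 0.12 to 0.73 and the limit fell by 0.09 to 0.60 points. One verdict changed: 34/38, from 75.1% to 74.9%.

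**3. Degrees of freedom.** With variance zero, replacing z by t on an assumed 46 df raises the bar at n = 24, 28, 33, 38, 44 and 49. For example, 26/28 moves from 75.5% to 74.8%, and at n = 24 nothing passes.

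**4. Interval, variance zero, z, no covariates.** Lower limit = expit{logit(x/n) − 1.96 √[1/x + 1/(n−x)]}.

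- 22/23: expit(3.091 − 1.96 × 1.022) = 74.8%, fail.
- 23/24: expit(3.135 − 1.96 × 1.022) = 75.6%, pass.
- n/n: the logit is infinite. For n = 24, as the fitted logit rises through 5, 8 and 10, the limit falls from 52% to below 0.001%.

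No class below 24 can therefore pass. Clopper-Pearson passes at 13/13 (75.3%), 19/20 (75.1%) and 22/23 (78.1%); below 13 neither interval can pass. For n = 24 to 50 both need the same number of successes, except that exact needs one fewer at n = 27. Apart from n = 27, the difference in that range is the all-success outcome.

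Binomial probability of passing, exact v Wald:

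| Class size | True rate 80% | 85% | 90% | 95% |
|---|---|---|---|---|
| 20 | 6.9% v 0% | 17.6% v 0% | 39% v 0% | 74% v 0% |
| 24 | 3.3% v 2.8% | 10.6% v 8.6% | 29% v 21% | 66% v 37% |
| 30 | 4.4% v 4.3% | 15.1% v 14.4% | 41% v 37% | 81% v 60% |
| 40 | 7.6% v 7.6% | 26.3% v 26.2% | 63% v 61% | 95% v 82% |

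At n = 24 the probability that all succeed is 0.5%, 2%, 8% and 29% at true rates of 80%, 85%, 90% and 95%. The Wald rule's chance of passing falls from 37% to 30% as the true rate rises from 95% to 98%.

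**5. Non-completers.** 24/24 has an exact lower limit of 85.8%. With two dispensed non-completers counted as unsuccessful, 24/26 gives 74.9%.

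**The case against.** The strongest reply is that the random effect does little in practice. In the one set of fits that estimated a variance, 1 of 229 verdicts changed. The 35/40 flip uses SDs that were imposed, and it needs the conditional mean: averaging the SD 1 limit over the random effect gives 73.8%, which fails as at SD 0. This is fair. It limits the flip to one family of fits, but the plan does not rule that family out.

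Logit-Wald is an inference, since 14.5 names no interval type. It is the ordinary reading. A fit stopped after two or three iterations at 38/38 would print a limit of about 82% to 83%, but the result would then depend on an unstated stopping rule.

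Kenward-Roger could be carried back from 14.6, which says it uses the method of 14.5. One sentence would settle that; 14.5 itself does not refer to it.

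At true rates of 80% to 85% and classes of 24 or more, the two intervals differ little. The practical weight rests on small classes and high success rates, and class size is unknown. The non-completer point concerns the analysis set; it is included because that set decides how often an all-success class arises.

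Finally, the study is exploratory and unpowered, and 14.10 allows documented changes. That lowers the stakes, but 14.5 still sets a superiority rule and 14.4 claims a 5% error rate.

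**Conclusion.** The concern holds and should be fixed; confidence is high. The subject random effect cannot be estimated from one outcome per subject. Under a likelihood fit with a non-zero SD, a borderline primary verdict can turn on choices the plan does not state. Under variance zero or restricted pseudo-likelihood its effect is at most 0.60 points in the outcomes tried.

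The larger defect is the interval. Read as logit-Wald with z and no covariates, it makes 75% unreachable in any class below 24 and unreachable by an all-success class of any size. The loss is small at true rates near 80% to 85% in classes of 24 or more. It is large at 95%: 29 points at n = 24 and 13 points at n = 40. All-success is not the expected result unless the true rate is high or the class is small.

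**What to change.** In 14.5, drop the subject random effect. Test hypothesis 2.3 with the observed proportion successful in the discontented-and-driven class and its two-sided Clopper-Pearson 95% interval against 75%, stating numerator and denominator in the population named in 14.2.

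Repeat the test in all subjects dispensed study lenses, counting non-completers as unsuccessful as 2.2 requires, and define that set in 14.3. The ITT set as written will not serve: enrolment is at consent (4.3), and the Quest questionnaire (step 1.10) precedes the eligibility decision (step 1.20). Screen failures who never wore a lens could therefore count as unsuccessful.

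Keep the Quest comparison for objective 2.1, with covariates, as an ordinary or Firth-penalised logistic regression. In 14.6, drop the random effect and the Kenward-Roger degrees of freedom.

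The cost is SAP wording, one set definition and a few lines of code. The test of hypothesis 2.3 becomes unadjusted. That matches 2.3, where only the secondary hypothesis asks for a result "significantly correlated with the success classification of the subjects after adjusting for age, sex and ADD power". The exact interval is slightly conservative: at a true rate of 75% it passes at most 2.4% of the time for n = 13 to 50, against a nominal 2.5%.

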14.6. Secondary Analysis

Likelihood to be a successful lens wearer vs. physical ocular related measurements

The secondary analysis will be conducted using the same method as described in Section 14.5 regarding CLUE vision score at baseline. In the model the CLUE vision score at baseline will be replaced by the secondary endpoints (defined in Section 2.2) one at a time to determine the significance level of each physical ocular related measurement. If the measurement is taken by eye, average value of the left and right eye will be used.

Kenward and Roger⁶ method will be used for the calculation of the denominator of degrees of freedom.

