14.7. Other Exploratory Analyses

Not Applicable.

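### The primary objective asks whether Quest classification is associated with success, but the only stated conclusion rule tests one Quest class against 75%

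*Combined protocol and SAP*

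**What the plan says.** - **Objective (synopsis and 2.1):** "To determine if the QUEST questionnaire, collected at baseline, are significantly correlated with subject groups" classed as likely to be successful or unsuccessful with the study lens.
- **Primary hypothesis (2.3):** "At least 75% of the subjects who are classified by Quest questionnaire as being" discontented and driven will fall in the likely-successful group.
- **Model (14.5):** success is a binary response in a generalized linear mixed model with a logit link, with "Quest questionnaire classification as the fixed effect; and subject as the random effect". Age, sex and add power may be added as covariates.
- **Decision rule (14.5):** the success proportion in the discontented-and-driven class is estimated with a 95% CI, and then: "If the lower limit of the CI is greater than 75%, the statistical superiority will be concluded". This is the only inferential statement in the section.
- **Error rate (14.4):** 5% overall for all planned analysis, with no primary test named.
- **Secondary analysis (14.6):** the secondary endpoints enter the model one at a time "to determine the significance level of each physical ocular related measurement".
- **Other exploratory analyses (14.7):** "Not Applicable".
- **Sample size (14.2):** 75 to enrol and 50 to complete; "the sample size was not determined based on any power analysis with regard to the primary endpoint".

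**The concern.** Correlation between Quest and success is a comparison: does the success rate differ between Quest classes? The 14.5 rule makes no comparison. It sets one class against a fixed 75%, and the other classes' success rates do not enter the criterion. Hypothesis and rule agree with each other; the gap lies between both of them and the objective.

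The Quest effect is in the model, so an association test could be produced. But 14.5 does not say whether that would be an overall test across classes or a contrast of one class with the rest, what effect measure would be reported, or what would be concluded. Those choices stay open until the data are seen. Meanwhile the one conclusion that is fixed in advance answers a different question from the one the study was set up to ask.

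**Working it through.** There is no planned power or sample-size figure to reproduce, because 14.2 says none was calculated. The check is whether the 14.5 rule and an association test can disagree, and how easily.

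**Inputs.** From the documents: threshold 75%, 95% CI, 50 completers. Assumed, because the documents give none: class sizes, success rates, no covariates, and all other Quest classes pooled.

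**Formulas.** The exact (Clopper-Pearson) lower limit for x successes in n is the 0.025 quantile of Beta(x, n − x + 1). It stands in for the unadjusted model-based limit. As a cross-check, the logit-Wald lower limit is the inverse logit of ln[x/(n − x)] − 1.96 × √[1/x + 1/(n − x)]. Association is tested by two-sided Fisher exact test.

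**Case 1: no association, rule passes.** 24/25 in the class, 24/25 in the rest.
- Exact lower limit: Beta(24, 2) at 0.025 = 0.796, above 0.75.
- Logit-Wald: ln(24) = 3.178; SE = √(1/24 + 1) = 1.021; 3.178 − 1.96 × 1.021 = 1.178; inverse logit 0.765, above 0.75.
- Risk difference 0; Fisher p = 1.00.

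**Case 2: strong association, rule fails.** 20/25 in the class, 8/25 in the rest.
- Exact lower limit: Beta(20, 6) at 0.025 = 0.593, below 0.75.
- Logit-Wald: ln(20/5) = 1.386; SE = √(1/20 + 1/5) = 0.500; 1.386 − 0.980 = 0.406; inverse logit 0.600, below 0.75.
- Odds ratio (20 × 17)/(5 × 8) = 8.5; risk difference 0.80 − 0.32 = 0.48 (Newcombe 95% CI 0.21 to 0.67); Fisher p = 0.0014.

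These two cases establish the point. The table shows that such disagreement is not confined to unusual data. It uses 50 subjects and full binomial enumeration; rates are for the class versus the rest.

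| Class / rest | Rule passes, 95% vs 95% | Rule passes, 85% vs 45% | Fisher power, 85% vs 45% | Fisher power, 85% vs 65% |
|---|---|---|---|---|
| 15 / 35 | 46% | 9% | 71% | 21% |
| 20 / 30 | 74% | 18% | 82% | 30% |
| 25 / 25 | 64% | 9% | 80% | 25% |
| 30 / 20 | 81% | 15% | 82% | 32% |
| 40 / 10 | 95% | 26% | 71% | 28% |

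With 95% success in both groups, Fisher rejects in 0.1% to 1.8% of trials. The power columns are for the one-class-versus-rest contrast only. Power of an overall test depends on the number of Quest classes, which is not visible in the public documents.

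**The case against.** The strongest reply is that the association analysis is already there. The 14.5 subsection is titled as success against Quest classification, the model has Quest as a fixed effect, and 14.4 sets the error rate. A reader might infer from the decision rule that the plan contains no analysis of association at all. The documents do not support that: the model is planned, and what is missing is a named test and its role.

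A reader might also take 14.6, which asks for a significance level for each secondary predictor, as proof that a Quest test was deliberately left out of 14.5. That is weak evidence. Section 14.6 borrows its method from a CLUE vision score analysis in 14.5 that, according to the amendment log, Amendment 8 removed. It can equally suggest that the 14.5 type of model was always meant to yield a significance level.

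Two more points have force. The Quest classes are in an appendix that is not shown; with only two classes, the overall test and the one-class contrast are the same and that ambiguity disappears. And the study is exploratory and unpowered, with its data meant for designing later work.

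What survives is that the written conclusion rule does not depend on the other classes, however many there are, and so cannot answer the objective as worded. Being exploratory limits the consequence but does not make objective and conclusion match.

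**Conclusion.** The point holds as a mismatch between the primary objective and the primary conclusion, and it should be fixed before database lock. That the rule can pass with no association and fail with a strong one follows from its form; the worked counts only illustrate it. How often this would happen depends on class sizes and rates that had to be assumed, so the table is not a forecast for this trial.

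A reader might go further and conclude that passing the rule would be presented as validating Quest as a predictor. No document says so, and the exploratory purpose in 14.2 argues against treating this as a fatal flaw. The per-protocol restriction in 14.2 is a separate matter that neither option below resolves.

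**What to change.** Choose one option before database lock.

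**(a) Keep the association objective.** In 2.3 and 14.5, name one two-sided 5% test of the Quest effect as the test of the primary objective. One suitable choice is discontented-and-driven versus all other classes, with odds ratio and risk difference and their 95% CIs. Keep the 75% criterion, with its CI, as a separately labelled benchmark and not a second primary conclusion, so that the overall 5% in 14.4 still holds.

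**(b) Keep the 75% rule as the primary conclusion.** Reword 2.1, the synopsis and the 14.5 subsection heading to the one-class question, and draw no conclusion about association.

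**Under either option:**
- Fit ordinary logistic regression with one row per subject. Section 2.2 defines one binary outcome per subject, so a subject random effect cannot be separately estimated.
- Make the matching edit in 14.6, which inherits the 14.5 method and specifies Kenward-Roger degrees of freedom.
- Write out the binary coding of success in 14.5 in place of the reference to a previous analysis, and replace the CLUE vision score reference in 14.6. Both point to the subsection removed by Amendment 8.

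**Cost.** Wording only; no change to data or visits. Under (a), the 75% statement is no longer the sole primary conclusion, and power for a modest gap is low: about 21% to 32% for 85% versus 65% with 50 subjects, under the assumed class sizes. Under (b), the association question is given up.

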14.6. Secondary Analysis

Likelihood to be a successful lens wearer vs. physical ocular related measurements

The secondary analysis will be conducted using the same method as described in Section 14.5 regarding CLUE vision score at baseline. In the model the CLUE vision score at baseline will be replaced by the secondary endpoints (defined in Section 2.2) one at a time to determine the significance level of each physical ocular related measurement. If the measurement is taken by eye, average value of the left and right eye will be used.

Kenward and Roger⁶ method will be used for the calculation of the denominator of degrees of freedom.

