		
 Subjects will be instructed to wear their glasses (if applicable) when not wearing the study lenses. 
Note: In the event a lens is lost or damaged, if no spare lenses are available, the subject will return to the investigator site for replacement. As much as reasonably possible, a damaged lens should be returned to the investigational site and then returned to the Sponsor. If lens damage is present, complete the Product Quality Complaint Form. The lens will be stored in labeled vial with sterile saline and returned to the Sponsor.
	
3.25.	Wearing Schedule	
The test lenses will be worn on a daily wear, daily disposable basis.
 
Note: For this protocol a day of wear is considered to be a minimum of 6 hours. When not wearing the study lenses the participant should be instructed to only wear their glasses (if applicable). For the follow-up visit instruct the participant they must have worn the lenses for at least 2 hours.
	
3.26.	Follow-up	The participant will be scheduled to return for their follow-up (V4) appointment in 1 week \pm 3 days from visit #3.	

VISIT 4

The Subjects must present to Visit 4 wearing the study contact lenses for at least 2 hours prior to the visit. If the subject has not worn the lenses for at least 2 hours the subject should be rescheduled.

Visit 4: Treatment 1 Follow-up 2 (2-week follow up)			
Step	Procedure	Details	
4.1.	Adverse Events and Concomitant Medications Review	Record any changes in concomitant medications and any adverse events that may have occurred since the last scheduled study visit.	
4.2.	Subject Reported Ocular Symptoms	If the participant reports ocular symptoms with their lenses, they will be recorded in the Subject Reported Ocular Symptoms eCRF	
4.3.	Wear time and Compliance	Subject's compliance with wearing the study CLs will be recorded.	

Visit 4: Treatment 1 Follow-up 2 (2-week follow up)			
Step	Procedure	Details	
		Record the hours/day and day/ week the participant has worn the study lenses and CL wear time on the day of follow-up.	
4.4.	Follow-up PRO (CLUE) Questionnaire	Subjects will complete the PRO (CLUE) Contact Lens performance questionnaires.	
4.5.	Subjective Acceptance	Record whether the subject's distance and near vision with the lenses is acceptable. Note: If the subject's distance and/or near vision is not acceptable with the study lenses the subject will be discontinued. Complete the Final Evaluation.	

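### The plan promises an overall 5% type I error, but the secondary hypothesis is met if any one of 15 separately tested endpoints is significant, with no multiplicity control

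*Combined protocol and SAP*

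**What the plan says.** - **Section 14.4:** "All planned analysis for this study will be conducted with an overall type I error rate of 5" percent.
- **Section 2.3, the rule for the secondary claim:** "At least one of the secondary endpoints will be significantly correlated with the success classification of the subjects". The same sentence names age, sex and add power as adjustment variables. That is covariate adjustment, not a correction for multiple testing.
- **Section 2.2:** 15 secondary endpoints. Several hold more than one variable; logMAR acuity alone covers three distances, monocular and binocular.
- **Section 14.6:** the endpoints go into the model "one at a time to determine the significance level of each physical ocular related measurement". Right and left eyes are averaged, so eyes do not double the count. The variable and visit to be used for each endpoint are not named. The model is taken from a Section 14.5 analysis of baseline CLUE vision score.
- **Section 14.5:** the current text has only the Quest analysis, with a subject random effect. Its decision rule is: "If the lower limit of the CI is greater than 75%, the statistical superiority will be concluded". Nothing links this rule to the secondary tests.
- **Section 14.2:** the study is exploratory and has no power calculation. "All analysis will be conducted on the per-protocol population defined in section 14.3".

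**The concern.** An any-of-15 rule with separate unadjusted tests does not give an overall 5%. One ocular measurement with p below 0.05 could be reported as a met hypothesis under an error rate that the plan does not control. A false predictor could then be carried into the later studies that Section 14.2 mentions.

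The number of failures analysed also matters. At Visits 4 and 5 (Section 7.2, steps 4.5 and 5.5), if distance and/or "near vision is not acceptable with the study lenses the subject will be discontinued". Such a subject is a failure under Section 2.2. The per-protocol set, however, is "All Subjects who have successfully completed all visits and did not substantially deviate from the protocol" (Section 14.3), so this failure leaves the data set used for all analysis and few failures may remain.

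Two lesser defects affect the same tests. The CLUE analysis that Section 14.6 borrows is not in Section 14.5. And reading addition is part of one tested endpoint, while Section 2.3 also names ADD power as a covariate.

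**Working it through.** **Inputs from the plan.** Overall error 5% (14.4); 15 endpoints (2.2); success if at least one is significant (2.3); separate tests (14.6); 50 subjects planned to complete (14.2).

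**Assumptions.** 0.05 two-sided per test (no per-test level is stated), one variable per endpoint, no true predictor. Correlations and failure counts are not in the documents, so ranges are shown.

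**Step 1: the plan's own figure.** With k independent tests at 0.05, the chance of at least one false positive is 1 − 0.95^k. For k = 1 this is 5%. The stated rate is reproduced only for a single test.

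**Step 2: 15 independent tests.** 1 − 0.95^15 = 0.537, with 15 × 0.05 = 0.75 false positives expected. Adding the primary test at one-sided 0.025 gives 1 − 0.975 × 0.95^15 = 0.548.

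**Step 3: 15 equally correlated normal tests.** The chance is 46%, 36%, 26% and 14% at correlation 0.3, 0.5, 0.7 and 0.9.

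**Step 4: small-sample logistic tests.** Success was simulated on endpoint, age, sex and ADD, without a random effect. Age–ADD correlation was assumed to be 0.5; the test was a Wald t with n − 5 df; 3,000 runs per cell. Chance of any significant result (%):

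| Analysed | Failures | corr. 0 | 0.5 | 0.7 | 0.9 |
|---|---|---|---|---|---|
| 50 | 15 | 45.7 | 32.3 | 23.8 | 11.3 |
| 50 | 10 | 42.9 | 29.6 | 21.7 | 11.8 |
| 50 | 6 | 37.2 | 23.9 | 17.5 | 10.2 |
| 50 | 4 | 18.4 | 14.7 | 10.1 | 6.3 |
| 50 | 3 | 4.4 | 3.6 | 3.1 | 1.8 |
| 40 | 15 | 45.0 | 29.3 | 22.2 | 10.9 |
| 40 | 10 | 41.5 | 28.1 | 20.3 | 10.7 |
| 40 | 6 | 31.1 | 21.0 | 16.1 | 8.5 |
| 40 | 4 | 10.6 | 8.8 | 6.7 | 4.0 |
| 40 | 3 | 1.5 | 1.4 | 1.4 | 0.9 |

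For 6 to 15 failures the ratio to the stated rate runs from 8.5/5 = 1.7 to 45.7/5 = 9.1.

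**Step 5: why the low cells are no comfort.** With 50 analysed, per-test error is 0.003 at 3 failures and 0.043 at 15. Power at 0.05 for an odds ratio of 3 per SD is 3% at 3 failures and 17% at 4. Error is low there because the test almost never rejects.

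**Step 6: more variables.** If the 15 endpoints became 30 variables (an assumed split by distance and by monocular/binocular), the chance is 1 − 0.95^30 = 78.5% if independent and 50.7% at correlation 0.5.

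**The case against.** The strongest reply is that this is an exploratory single-arm study with no power calculation, where unadjusted secondary p-values are ordinary. The primary rule is untouched, and the preferred remedy changes wording only. That limits the consequence, but it does not remove the conflict: neither Section 4.2 nor Section 14.2 withdraws the overall 5% or the at-least-one hypothesis.

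Second, the size is not fixed by the documents. The scenarios lie on both sides of 5%, and the 1.7-to-9 range uses 6 to 15 failures although few may remain. This is fair. Only the absence of control is certain; the size depends on the assumptions. The simulation is also a fixed-effects Wald model, not the mixed model the plan names.

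Third, some costs given below for keeping 5% depend on the method. A likelihood-ratio test at 0.0033 gives power of about 29/43/59% for 6/10/15 failures, against 0/1/14% for Wald, though its null rate is 0.005 to 0.008 rather than 0.0033. At 90% true success, exact or Wilson limits open the primary gate 39% of the time with 20 subjects; with 25 it is 27% (exact) or 54% (Wilson). These figures stand. The Wald and logit-scale figures are closer to the kind of model in Sections 14.5 and 14.6, and they bear only on the alternative fix.

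Fourth, Section 14.5 includes covariates only where appropriate, so ADD could already be dropped. Section 2.3 nevertheless names it without that qualification.

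**Conclusion.** The concern holds. Section 14.4 claims a property that Sections 2.3 and 14.6 do not have. At 0.05 per test and one variable per endpoint, the chance of wrongly meeting the secondary hypothesis is 54% under independence and 14% at correlation 0.9. In the Wald simulations with 6 to 15 failures it is roughly 9% to 46%. It comes near or below 5% only where the tests have almost no power. More variables or visits per endpoint would raise these figures. This should be fixed before analysis; the primary conclusion does not depend on it.

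**What to change.** **Preferred.**

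1. In 14.4, restrict the error statement to the primary test and state it as that test is built: the lower limit of a two-sided 95% CI against 75%, that is, one-sided 2.5%.
2. In 14.6, label the secondary p-values unadjusted and exploratory, and report how many tests were run.
3. In 2.3, reword so that one unadjusted significant endpoint is not a confirmed hypothesis.

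The cost is wording and a weaker secondary claim.

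**Under either option**, replace the CLUE reference in 14.6 with the model itself: success on the tested endpoint plus age, sex and ADD power, with no CLUE or Quest term, and ADD omitted when reading addition is the tested variable. State whether the subject random effect and Kenward-Roger are kept. With one success outcome per subject, the random-effect variance cannot be estimated separately.

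**Alternative, if 5% for all analyses is kept.** Name one variable and one visit per endpoint, and use Holm or permutation max-T over the 15. Either test this family at 5% only if the primary test succeeds, or split alpha 2.5%/2.5%.

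The cost is power. Simulated for an odds ratio of 3 per SD, 50 analysed, before any gate:

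| Threshold | 6 failures | 10 | 15 |
|---|---|---|---|
| 0.05 unadjusted, Wald | 47% | 72% | 84% |
| Smallest Holm step, 0.05/15 = 0.0033, Wald | 0% | 1% | 14% |
| Alpha split, 0.025/15 = 0.0017, Wald | 0% | 0% | 2% |
| Max-T at 5%, independent endpoints | 14% | 33% | 53% |

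A gate lowers this further. The size of the discontented-and-driven Quest class is not given. At an assumed 90% true success, with an unadjusted logit-scale interval (undefined if all succeed, counted as not passing), the gate opens 0% of the time with 20 such subjects, 20% with 25, 37% with 30 and 77% with all 50. For example, with 25 only 24 successes pass: 25 × 0.9^24 × 0.1 = 0.199. Gated power cannot exceed the smaller of the two figures.
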